8.2	Subject Population(s) for Analysis	32
9	Safety and Adverse Events	32
9.1	Definitions	32
9.1.4	Adverse Event	32
9.1.5	Serious Adverse Event	32
9.2	Recording of Adverse Events	33
9.3	Relationship of AE to Study	33
9.4	Reporting of Adverse Events, Adverse Device Effects and Unanticipated Problems	33
9.4.4	Follow-up report	33
9.4.5	Investigator reporting: notifying the study sponsor	33
9.5	Unblinding Procedures	34
9.6	Stopping Rules	34
9.7	Medical Monitoring	34
9.7.4	Data and Safety Monitoring Plan	34
10	Study Administration, Data Handling and Record Keeping	35
10.1	Confidentiality	35

10.2	Data Collection and Management	35
11	Study Monitoring, Auditing, and Inspecting	36
11.1	Study Monitoring Plan	36
11.2	Auditing and Inspecting	36
12	Ethical Considerations	36
12.1	Risks	36
12.2	Benefits	40
12.3	Risk Benefit Assessment	40
12.4	Informed Consent Process / HIPAA Authorization	40
13	Study Finances	41
13.1	Funding Source	41
13.2	Conflict of Interest	41
13.3	Subject Stipends or Payments	41
14	Publication Plan	41
15	References	41
16	Attachments	54
17	Appendix	55
17.1	Magventure MagPro Manual	55

List of Abbreviations

AE: Adverse event

BAC: Biostatistics Analysis Center

CAT: Computerized Axial Tomography

CILT: Constraint Induced Language Therapy

DSMB: Data and Safety Monitoring Board

fMRI: Functional Magnetic Resonance Imaging

IFG: Inferior Frontal Gyrus

NAVS: Northwestern Assessment of Verbs and Sentences

PNT: Philadelphia Naming Test

PWA: Patients With Aphasia

SAE: Serious Adverse Event

SLT: Speech Language Therapy

TMS: Transcranial Magnetic Stimulation

WAB-(AQ): Western Aphasia Battery - (Aphasia Quotient)

Study Summary

Title	A Phase II, Randomized, Blinded Study of Transcranial Magnetic Stimulation and Constraint Induced Language Therapy for the Treatment of Chronic Aphasia
Short Title	TMS and CILT for Chronic Aphasia
IRB Number	831532
Phase	Phase 2
Methodology	Randomized, Blinded, Sham-Controlled
Study Duration	5 years
Study Center(s)	University of Pennsylvania
Objectives	
Primary: To determine if the combination of TMS and CILT is more effective than sham TMS and CILT as a treatment for chronic aphasia from stroke.
 
Secondary: To identify anatomic and behavioral predictors of response to treatment and the mechanism underlying the beneficial effect of the treatment.

Number of Subjects	75 subjects
Main Inclusion and Exclusion Criteria	Proficient English speakers with a single left hemisphere stroke causing aphasia will be included. Main exclusion criteria are multiple infarcts, history of head trauma, psychiatric illness, and substance abuse and contraindications to TMS.
Investigational Product (drug, biologic, device, etc.)	TMS will be delivered using a MagVenture MagPro X100. 1200 pulses of 1 Hz repetitive stimulation at 90% motor Threshold at inferior pars triangularis during 10 sessions over 2 consecutive weeks
For Device include the planned use	

**For Drug, food,
cosmetic, etc.
include the dose,
route of
administration and
dose regimen**

**Duration of
administration (if
applicable)**

10 sessions of 20 minutes 1 Hz stimulation at 90% Motor Threshold

Reference therapy

There is no standard reference therapy for repetitive transcranial magnetic stimulation; this regimen has been used in many similar published studies, including our own work with patients with aphasia

**Statistical
Methodology**

Linear Mixed Models will be used to compare the performance of subjects receiving TMS to subjects receiving sham TMS on change in WAB-AQ scores

Safety Evaluations

Subject reports of adverse events will serve as the primary measure of safety.

**Data and Safety
Monitoring Plan**

A Data and Safety Monitoring Committee consisting of 3 individuals with experience with aphasia and/or non-invasive brain stimulation will serve as the DSMB. The BAC group, under the guidance of the faculty statisticians, will provide safety reports every six months to this monitor and the PI. These reports will be blinded as to treatment assignment, unless unblinding for individual events is requested by the DSMB. All SAEs will also be reported to the IRB.

Sub-Study Summary

Title

A Phase II, Randomized, Blinded Study of Transcranial Magnetic Stimulation and Constraint Induced Language Therapy for the Treatment of Chronic Aphasia – Alzheimer Disease Sub-study

Short Title

Alzheimer Disease Sub-study

IRB Number 831532

Phase Phase 2

Methodology Randomized, Blinded, Sham-Controlled

Study Duration 2 years

Study Center(s) University of Pennsylvania

Objectives

Primary: To determine if the combination of TMS and CILT is more effective than sham TMS and CILT as a therapy for impaired verbal communication in Alzheimer Disease.

Secondary: To identify anatomic and behavioral predictors of response to treatment and the mechanism underlying the beneficial effect of the treatment.

Number of Subjects 30 subjects

Main Inclusion and Exclusion Criteria Proficient English speakers with mild-moderate Alzheimer Disease. Main exclusion criteria are history of stroke, seizure, or other significant neurologic disease, significant depression, and substance abuse and contraindications to TMS.

Investigational Product (drug, biologic, device, etc.) TMS will be delivered using a MagVenture MagPro X100. 30 two-second trains of 10 Hz TMS every 30 seconds at left inferior parts triangularis and at left posterior superior temporal gyrus at 100% motor threshold during 10 sessions over 2 consecutive weeks

For Device include the planned use

For Drug, food, cosmetic, etc.

include the dose,

route of

administration and

dose regimen

Duration of administration (if applicable)	10 sessions of 2 minutes overall of 10 Hz stimulation at 100% Motor Threshold
Reference therapy	There is no standard reference therapy for repetitive transcranial magnetic stimulation; this regimen has been used in many similar published studies.
Statistical Methodology	Linear Mixed Models will be used to compare the performance of subjects receiving TMS to subjects receiving sham TMS on change in WAB-AQ scores
Safety Evaluations	Subject reports of adverse events will serve as the primary measure of safety.
Data and Safety Monitoring Plan	A Data and Safety Monitoring Committee consisting of 3 individuals with experience with aphasia and/or non-invasive brain stimulation will serve as the DSMB. The BAC group, under the guidance of the faculty statisticians, will provide safety reports every six months to this monitor and the PI. These reports will be blinded as to treatment assignment, unless unblinding for individual events is requested by the DSMB. All SAEs will also be reported to the IRB.

BACKGROUND AND STUDY RATIONALE

This document is a protocol for a clinical research study. This study will be conducted in full accordance with all applicable University of Pennsylvania Research Policies and Procedures and all applicable Federal and state laws and regulations including US and international standards of Good Clinical Practice.

Introduction

Aphasia is an acquired disorder of language that occurs in approximately 30% of individuals with stroke and impacts approximately 1 million Americans (see NINDS.NIH.gov). Persons with aphasia (PWA) suffer greater disability and utilize more health care resources than individuals with stroke without aphasia (33); Boehme et al (16), for example, estimated that aphasia adds \$2.16 billion annually to the cost of acute stroke care. The economic burden of aphasia can persist for years, not only due to direct costs of care, but also because of lost wages and productivity. Furthermore, the social isolation felt by PWA leads to enormous personal and psychological costs. Current treatments for aphasia are only modestly beneficial (17, 59). Many individuals with moderate or severe aphasia after stroke continue to suffer significant impairment despite therapy. The fundamental objective of this proposal is to demonstrate that Transcranial Magnetic Stimulation (TMS) paired with language stimulation will improve chronic aphasia. More specifically, we seek to demonstrate that TMS combined with speech-language therapy (SLT) will improve language performance more than SLT alone. Additionally, we will employ modern techniques for network analyses of neuroimaging data collected before and after TMS and SLT to determine the mechanism(s) by which this is achieved. Finally, we seek to identify the predictors of response to TMS, making use of genetic testing. To achieve these goals, we propose the first double-blind, placebo-controlled investigation of TMS combined with SLT that is sufficiently powered to assess the efficacy of the therapy. If the treatment proves successful, our work will set the stage for a Phase 3 trial of the efficacy of TMS with SLT in the treatment of chronic aphasia.

AD Sub-study Introduction

Alzheimer Disease (AD) afflicts more than 5 million people in the USA at present; this number is expected to rise to 13.5 million by 2050 because of the aging of the population and increases in life expectancy. Impaired verbal communication is a hallmark of AD and represents a major cause of distress and disability (162, 165). This impairment reflects, at least in part, deficits in core language faculties (e.g. phonology, lexical representations and semantic memory (154, 175). There is a paucity of treatments for these impairments. In light of the emerging literature demonstrating that TMS improves general cognition in subjects with AD, we propose to extend our ongoing study of the effectiveness of TMS and speech therapy for treatment of post-stroke aphasia to the issue of impaired verbal communication in subjects with AD. This sub-study will be a double blind, randomized study of subjects with mild-moderate AD to explore the effectiveness of TMS as a therapy for impaired verbal communication. Except when indicated below, the intervention for subjects with AD is identical to the main study,

1.1 *Background and Relevant Literature*

In the first series of studies of TMS as a treatment of aphasia, Naeser and colleagues delivered inhibitory TMS to the right hemisphere. This decision was motivated by the hypothesis that residual language is supported by the left hemisphere but that the residual left hemisphere structures are inhibited by the intact right hemisphere (70, 86; see also 51, 133, Figure 1A). Predicated on the same assumption, many investigators have attempted to treat chronic aphasia with inhibitory (1 Hz) TMS to the right IFG.

A large body of small studies and several meta-analyses provides proof of concept that TMS can be of substantial benefit in treating chronic post-stroke aphasia. The studies are small, however, and have differed with respect to a number of parameters (e.g., stimulation site, duration of therapy, presence or absence of concurrent speech therapy) so the benefit of TMS for chronic aphasia has not been established. We propose a well-powered randomized, controlled, treatment experiment that will test for the first time whether inhibitory TMS of the right pars triangularis, when coupled with CILT, yields greater language improvement 3 and 6 months later, relative to sham TMS and CILT.

TMS is a technique by which a brief electrical current is induced in brain tissue causing a brief suppression of the excitability of the underlying tissue; the technique, which was introduced in the 1980s and has been extensively used around the world, has been shown to transiently improve or disrupt specific cognitive operations. To achieve this end, a coil is positioned against the subject's head. The delivery of a single pulse begins with the discharge of current from a capacitor into a circular or figure-of-eight coil; this electrical current generates a brief magnetic field of up to 2.2 Tesla. As the pulse of electricity has a rise time of 0.2 ms. and a duration of 1 ms., the magnetic field changes in intensity quite rapidly. Because the magnetic field passes freely through the scalp, skull, and meninges, the flux in the magnetic field induces a small electric field in the brain that transiently alters neural activity.

TMS may be delivered in a variety of ways. In this study we propose to use 1 Hz TMS; that is, TMS pulses will be delivered at a frequency of 1/second. This style of TMS is assumed to be inhibitory in that it transiently suppresses the function of the cortex under the coil. Using the figure-of-eight coil to be employed here, TMS is thought to reduce activity in approximately 1 cubic cm. of cortex. Many investigators have employed TMS with a frequency of 1 Hz for periods of 20 minutes and longer; mild behavioral deficits are often present for several minutes in these studies.

1.1.1 Clinical Data to Date

TMS has also been used to treat a variety of conditions such as hemiparesis and depression. More relevant to the current application, more than 20 studies (see 25 and starred items in reference list) involving approximately 250 subjects have investigated whether TMS can improve language performance in Persons with Aphasia (PWA). Positive results have been reported in most of these studies and confirmed in several published meta-analyses (66, 91, 103, 118). Our group has also reported positive results from a randomized cross-over study of 10 subjects treated with 1 Hz TMS to the right inferior frontal gyrus (IFG). We found a significant improvement in picture naming after real but not sham TMS that was maximal at 6 months after the completion of therapy (76; see also 47, 49). The Standard Difference of Means (SMD; a measure of effect size) between the real and sham treated groups in our study, to which the current proposal is similar, was approximately 1.1 (119). As will be discussed at length below, there have been no adverse effects from TMS in any of the previous 20+ studies of TMS to treat aphasia.

1.2.2.1 Time course of TMS Benefits

Evidence suggests that the benefit from TMS to the right IFG increases over time in the absence of ongoing therapy (10, 84, 86). We reported a similar finding in a subject followed for 10 months after TMS (47). As most studies assess treatment efficacy 2 months or less after treatment, there is reason to think that many studies reported to date (e.g., 1, 116, 127) have underestimated the benefit from TMS. Our proposed study will measure treatment-related outcomes at 3 and 6 months, with the expectation that the advantage for the TMS-treated group will be maximal at 6 months.

1.2.2.2 Coupling of TMS with SLT

There is strong evidence from studies of motor rehabilitation that TMS and behavioral treatments produce synergistic effects in subjects with brain lesions, presumably by enhancing use-dependent plasticity (122). For example, Avenanti et al. (6) demonstrated that subjects with chronic hemiparesis exhibited significantly greater benefit from occupational or physical therapy paired with real as compared to sham 1 Hz TMS over the intact hemisphere. In a number of studies, the improvement with TMS was greater when TMS was delivered before, as compared to after, physical or occupational therapy (see 7, 56, 65 for similar results). In light of these data, the proposed study will couple TMS with SLT in a manner designed to maximize use-dependent plasticity.

1.2 AD Sub-Study Background

TMS has been used to enhance cognition, including language, in normal subjects () as well as subjects with focal brain injury (46, 76). In recent years, TMS has also been demonstrated to enhance cognition in subjects with AD (27, 148, 149, 150, 160, 163, 170, 171) and Mild Cognitive Impairment (155). The majority of studies have assessed the impact of TMS on “general cognition,” usually as assessed by broad measures of cognition such as the Alzheimer Disease Assessment Scale – Cognitive subscale (ADAS-Cog;106); Koch et al. (163), however, demonstrated significant benefit on memory from repetitive TMS to the precuneus and Wu et al. (179) demonstrated that TMS improved psychiatric symptomatology in AD. Only one study reported data regarding the impact of TMS on language; in a study that explored the effects of TMS on general cognition and memory, Cotelli et al. (27) reported limited data from language tasks. They found that TMS improved performance on a sentence comprehension task.

Two recent reviews and meta-analyses also point to the utility of TMS as a treatment in AD. Cheng et al. (52) reported a meta-analysis of 8 randomized, controlled trials including 194 participants (107 with active treatment and 87 with sham) demonstrating a moderate effect of TMS (SMD-0.48, 95% CI, 0.12-0.84). Vacas et al. (176) reported a meta-analysis of the effects of TMS on behavioral and psychological symptoms from 4 randomized, controlled trials involving non-invasive brain stimulation; they found a significant benefit in studies involving TMS but not tDCS.

It is important to note that TMS was well tolerated in all studies. Several investigators reported minor headache and “non-specific minor discomfort” (see 152 for a review). We are unaware of major adverse events in any study and there is no report of a subject withdrawing from a study because of adverse events.

1.3 Dose Rationale (if applicable)

We propose to administer 1200 pulses of TMS at 90% motor threshold on 10 occasions (Monday-Friday on consecutive weeks). This schedule was selected because it was employed in most of the studies, including our work (47), that demonstrated a beneficial effect from TMS on language function.

1.3.1 AD Sub-Study Dose Rationale

We propose to administer 1200 pulses of TMS at 100% motor threshold on 10 occasions (Monday-Friday on consecutive weeks). This schedule was selected because it was employed in most of the studies, including our work (47), that demonstrated a beneficial effect from TMS on language function. We propose to employ “rapid” rTMS because Ahmed et al (148) demonstrated that rapid rTMS produced benefit in the ADAS-Cog in patients with AD whereas 1 Hz rTMS did not. The decision to stimulate at 10 Hz is motivated by the fact that several studies demonstrating benefit on the ADAS-Cog in subjects with AD employed this frequency (149, 150, 164, 170, 171). Most studies to date have delivered 1200 pulses per session. We note that the stimulation parameters that we propose are within guidelines set forth by Rosse et al (106).

1.3.2 Clinical Studies in Children

We propose to include subjects >18 years of age. We do not have access to children with stroke and there is relatively little experience with TMS in children. Furthermore, as studies to date demonstrating benefit from TMS for aphasia were performed in adults, there is no evidence of efficacy of the treatment in aphasic children.

2 Study Objectives

2.1 Primary Objective

- To demonstrate that TMS combined with Constraint Induced Language Therapy (SLT) will improve language performance more than sham TMS and CILT.

2.2 Secondary Objectives (if applicable)

- To determine the mechanism(s) by which TMS improves language function using modern techniques for network analyses of neuroimaging data collected before and after TMS and CILT.
- To identify the predictors of response to TMS, including using genetic analysis.

3 Investigational Plan

3.1 General Design

The overall timeline for each subject's participation is indicated in Figure 1. Briefly, after randomization to treatment with TMS+CILT or sham TMS+CILT, all subjects will undergo baseline behavioral testing, neuroimaging, and genetic testing before receiving 10 treatment sessions over 2 weeks. Immediate post-treatment effects will be assessed within 4 days of the completion of therapy by repeating the baseline probes of treated and untreated stimulus sets from CILT. At 3 and 6 months after the completion of TMS, subjects will return for follow-up assessments during which the same tasks administered in Visits 1 and 2 will be repeated. Subjects who are able to undergo MRI scanning will have anatomic and fMRI scans at T5 and T22. Subjects who are not able or willing to undergo MRI will undergo CAT scan of the head.

Figure 1: Timeline for each subject

Screening Visit	Baseline 1	Baseline 2	Baseline 3	Baseline 4	Treatment 1-10	Follow-up 1	Follow-up 2 & 3	Follow-up 4, 5, 6
Visit 1	Visit 2	Visit 3	Visit 4	Visit 5	Visit 6-16	Visit 17	Visit 18-19	Visit 20-22
-Informed Consent	-WAB	-WAB	-Leftover Testing	-MRI/CAT scan	Real or Sham TMS (20 min, 1hz at 90% MT) + CILT	-CILT probe	3-months: -same as Baseline 1 & 2	6-months: -same as Baseline 1 & 2 -MRI scan
-Inclusion/Exclusion Criteria	-PNT	-Ruff Figural Pyramids and Fluency Test	-Baseline will continue into 4th and 5th visits if necessary					
-Demographics History	-Pyramids and Palm Trees	-Word and non-word repetition						
-Medical History	-Communication Confidence	-Cinderella Story						
-Medical Intake								
-Geriatric Depression Scale	Scale	-CILT baseline						
120 minutes	120-180 minutes	120-180 minutes	60-180 minutes	120 minutes	90-120 minutes	60 minutes	120-180 minutes	120-180 minutes

3.1.1 Baseline Phase

The baseline phase will consist of 3 sessions, each lasting 1-2 hours depending on the stamina of the subject. The point of the baseline testing is to characterize the subject's language function. To that end, a number of standard language and neuropsychological tasks will be

administered. These include the Western Aphasia Battery (121), Pyramids and Palm Trees test (52), Figural Fluency Test (108), word and non-word repetition tasks, the Nicholas and Brookshire Narratives (88), CILT stimulus naming, and Northwestern Assessment of Verbs and Sentences (see below for details), as well as a measure of grip strength and finger flexibility. Additionally, during the baseline, subjects will undergo MRI of the brain or, if they have a contraindication to MRI, a CAT scan of the head. No contrast will be used. If they consent to DNA sampling, participants will also have a saliva sample taken for the purpose of genotyping.

All assessments listed are not mandatory. If the participant wishes to discontinue testing or refuses to perform a certain test due to frustration or fatigue, their request will be granted and not considered a deviation. Instead we will make note of any refused tests in our case report form (i.e. visit checklist).

3.1.2 Study Intervention Phase

In the treatment phase, there will be 10 TMS sessions over 2 consecutive weeks in which 20 minutes (1200 pulses) of 1 Hz TMS at 90% MT will be delivered to the inferior pars triangularis. Each TMS treatment session will be immediately followed by a 60-90 minute session of CILT.

3.1.3 Follow Up Phase

There will be two 3-month post-treatment visits and two 6-month post-treatment visits in which the full battery of language and cognitive assessments will be repeated. Subjects who are able to undergo MRI scanning will have anatomic and fMRI scans at or after the 6-month post-treatment visit.

All assessments listed are not mandatory. If the participant wishes to discontinue testing or refuses to perform a certain test due to frustration or fatigue, their request will be granted and not considered a deviation. Instead we will make note of any refused tests in our case report form (i.e. visit checklist).

3.1.4 Allocation to Interventional Group

Participants will be randomized to either TMS or sham TMS in a 2:1 allocation ratio using permuted blocks of variable size. Further, as it has been suggested that aphasia severity influences response to TMS treatment for aphasia, randomization will be stratified by WAB AQ score to ensure an approximately equal allocation of treatments among PWA with WAB AQ <50 and WAB AQ => 50 (see 60). The unblinded study coordinator will be responsible for generating the random numbers used to conduct the randomization.

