4.5 Subject Recruitment

Subjects will be recruited from several sources. The first source is from personal contacts within the University of Pennsylvania Health system, including neurologists, psychologists, neurosurgeons, and rehabilitation therapists. The study coordinator will receive referrals from members of UPHS who have previously agreed to identify potential individuals who meet the criteria of the database. The PI or study coordinator will then reach out to the subject or family member via in-person (i.e. at bedside), telephone, email, or letter to determine whether they wish to consent into the protocol. A second source is from the Penn Institute of Rehabilitation Medicine (PIRM). The study coordinator will have access to the medical charts of inpatients at PIRM and will prospectively and retrospectively review charts to determine if patients match the inclusion criteria of the protocol. Another source will be the Penn Data Store, where the study coordinator will review patient charts using the Cohort Explorer and Pennseek tools offered by the Penn Data Analytics team. Cohort Explorer will be used to identify patients that meet our inclusion/exclusion criteria. We will also use Pennseek to search free text within their chart for clinical impairments germane to currently recruiting studies (e.g. "aphasia", "stroke"). The study coordinator will send our query to the Penn Data Store, and work with the Penn Data Analytics team to refine our request. The study coordinator will request the names, telephone numbers, and addresses of patients. This data request will be automatically generated on a monthly basis. Another source is from subjects already enrolled in the Center for Cognitive Neuroscience (CCN) Focal Lesion Database (FoLD) or already listed in the FoLD Recruiting Database (covered by Protocol #824122). Whenever a researcher requests a subject enrolled into the FoLD Database under Protocol #824122, the Patient Coordinator will invite that patient to continue their participation in the database under the current protocol.

PWA will also be recruited from the Moss Rehab Research Institute (MRRI); [name] is a co-investigator at MRRI, and along with [name] CCC-SLP will recruit approximately 8-9 subjects with chronic aphasia annually.

Finally, [name], a consultant to the project, will refer potential participants from the Saffran Aphasia Center at Temple University. These potential subjects will then be contacted by study personnel.

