5.3 Blinding

Participants will not be informed of their assignment to active or sham status. Sham TMS will be administered with a sham TMS coil that looks and sounds like the active coil but does not generate a magnetic field. Surface electrodes applied to the scalp during sham stimulation will simulate the sensation of TMS, therefore allowing subjects with prior experience with TMS to be blind to condition as well.

The unblinded study coordinator will keep the master file of subject assignments. This individual will administer TMS, but all other individuals in contact with the subject or their data will be unaware of group assignment. In particular, the speech-language pathologist (SLP) and the individuals administering and scoring the language measures will not be present for the administration of TMS and will be blinded with respect to subject assignment. In the case of an adverse event, the blind may be broken if the PI deems it necessary.

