6.1 Screening

The screening visit will consist of:

- Informed Consent
- Review of the Inclusion/Exclusion Criteria
- Review of Demographics/Medical History
- Medical Intake (performed by the study PI or [name], both of whom are neurologists).
- In cases where the baseline visits will be conducted via tele-assessment, the Ruff Figural Fluency test may be administered at this visit.

The anticipated time of this visit is 30 minutes; depending on the subject's interest and responses to the screening tests, this visit could be combined with Visit 1 below.

An initial remote screening visit may be conducted via Bluejeans. Before screening and the medical intake, remote consent will be obtained, with e-signatures collected via RedCAP (explained in detail below). An in-person Medical Intake screening may occur after the remote consent and screening.

At the time of screening, or sometime afterwards, the Aphasia Depression Rating Scale (ADRS) will be completed by the patient's caregiver. The caregiver rates the subject on 9 different items. The ADRS has high reliability, sensitivity and specificity and is specifically designed for evaluation of aphasic patients (147). The ADRS will be given to the patient's caregiver to complete at the

time of screening, or will be mailed to the caregiver or close relative before the baseline screening. The ADRS will serve as a covariate in statistical analysis.

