12.6 Informed Consent Process / HIPAA Authorization

All subjects will be provided a consent form describing the study providing sufficient information for subjects to make an informed decision about their participation in this study. The nature and goals of the proposed research will be explained to the subjects and, as appropriate, to their families. The formal consent of a subject, using the IRB-approved consent form, must be obtained before that subject undergoes any study procedure. The subject must sign the consent form to participate. The Principal Investigator or study staff obtaining consent will additionally sign the form. Subjects will be consented by the study Principal Investigator, or appropriate designee, in a room we have selected in which to perform consent, which is located outside of the clinic. Potential subjects will review the consent form in detail with the person designated to consent and have the ability to take the consent home for further review. We note that the PI has worked with subjects with aphasia for more than 30 years and has extensive experience assessing the capacity of subjects with aphasia to provide and obtaining informed consent.

Since potential subjects will be recruited by phone, email or letter, and PHI will necessarily be collected to conduct screening, we will be using a verbal consent script which will be completed before any PHI is collected.

To reduce the burden of in-person visits during COVID-19, as well as for potential participants for whom travel for single visits is burdensome, we will conduct informed remote consent via

Bluejeans. The consent form will be provided through RedCAP survey webpage, and may also be shared as a pdf. The video call will involve identification of the participants of the call, and then will move into a full review of the IRB-approved consent form by either the Principal Investigator or study staff. The Principal Investigator will confirm that the participant is informed and willing to participate. The participant will then provide an e-signature via RedCAP; the document will then also be e-signed by the Principal Investigator or the study staff.

13 Study Finances

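### Allocation concealment is not assured: the unblinded coordinator makes the list, holds it and delivers TMS, and nothing keeps that person out of enrolment

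*Combined protocol and SAP*

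**What the plan says.** Sequence generation belongs to one member of the site staff: "The unblinded study coordinator will be responsible for generating the random numbers used to conduct the randomization" (3.1.4, repeated in 3.2.4). Section 5.3 adds custody of the assignments, "The unblinded study coordinator will keep the master file of subject assignments", and delivery of the treatment: "This individual will administer TMS, but all other individuals in contact with the subject or their data will be unaware of group assignment". The main study uses 2:1 variable-size permuted blocks, stratified by WAB AQ below 50 or at least 50. The Alzheimer sub-study uses the same ratio and blocking without strata.

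On recruitment to the main study, section 4.5 says "The PI or study coordinator will then reach out to the subject or family member", and that at the rehabilitation institute the study coordinator "will prospectively and retrospectively review charts to determine if patients match the inclusion criteria of the protocol". Neither sentence says whether this coordinator is blinded. Section 10.1 has the PI contact most candidates. On consent, section 12.6 says "Subjects will be consented by the study Principal Investigator, or appropriate designee".

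On timing, section 3.1 says that "after randomization to treatment with TMS+CILT or sham TMS+CILT, all subjects will undergo baseline behavioral testing, neuroimaging, and genetic testing". Section 3.2 gives the same order for the sub-study.

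**The concern.** Randomization protects against selection bias only if whoever decides on approach, eligibility or timing cannot foresee the next assignment. Here one person writes the sequence, stores it and applies it. If that person also has a hand in enrolment, candidates could be brought forward, delayed or passed over according to the arm that comes next. Variable block sizes hide the next assignment from other people, but not from the author of the list.

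The primary model in section 8.4.1 has one baseline covariate, WAB AQ. Selection on other prognostic features would not be corrected in the primary estimate unless they were related to WAB AQ. The sham arm has only about 25 evaluable subjects, so a few selected places could matter.

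**Working it through.** **1. Is there a concealment mechanism?** Sections 3.1.4, 3.2.4, 4.5, 4.6, 5.3, 5.5, 6.1, 6.2 and 12.6 mention no independent list, central or web allocation, or sealed envelopes. None excludes the unblinded coordinator from enrolment. The coil-number log in section 5.5 is completed by those who deliver TMS. Under section 5.3 that is the list holder, so the log is not an independent check. (Section 5.5 speaks of TMS technicians in the plural and section 5.3 of one individual; these need reconciling.)

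**2. Is the recruiting coordinator the unblinded one?** Sections 3.1.4, 3.2.4 and 5.3 use the qualifier unblinded; section 4.5 does not. Nothing equates the two roles and nothing separates them. Section 12.6 allows a designee to take consent without limiting who that may be. For the Alzheimer sub-study, section 4.6 recruits from the memory-center cohort and gives no coordinator a task. There, only the combined role of list maker, list holder and operator is established.

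**3. When is the arm known?** Sections 3.1 and 3.2 put randomization before baseline testing. In the main study the stratum needs a WAB AQ, and so does eligibility (AQ 20 to 85, section 4.1). The WAB is not among the screening items in section 6.1. It is first listed at Baseline 1 (6.3.1) and again at Baseline 2 (6.3.3). The plan does not say which score sets the stratum or when an assignment is released.

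**4. The plan's own sample size.** Inputs from section 8.3: effect 0.7 SD, alpha 0.05 (sidedness not stated; two-sided reproduces the figure), 80% power, 2:1 allocation.
- Sham n = (1 + 1/2) × (1.960 + 0.842)² / 0.7² = 24.03, rounded up to 25. With 50 on TMS the total is 75, as planned.
- Power at 50:25 is 0.815 by the normal approximation and 0.805 by the noncentral t. The plan reproduces.

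**5. Illustration of what an imbalance would do.** Inputs: SD of change 5.7 points (8.3) and 50:25 evaluable subjects. The imbalance is assumed.
- Standard error = 5.7 × √(1/50 + 1/25) = 1.396 points.
- With no true effect and an imbalance of b SD in expected change, the noncentrality is b / √(1/50 + 1/25) = b / 0.245, on 73 degrees of freedom.

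| Assumed imbalance | AQ points (b × 5.7) | Share of 4-point target | Two-sided type I error |
|---|---|---|---|
| 0 | 0 | 0% | 5.0% |
| 0.1 SD | 0.57 | 14% | 6.9% |
| 0.2 SD | 1.14 | 29% | 12.7% |
| 0.3 SD | 1.71 | 43% | 22.7% |

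An imbalance of 0.1 SD would arise, for example, if 10% of one arm (5 of 50 on TMS) differed by a full SD in expected change: 0.10 × 5.7 = 0.57. That is generous, because 5.7 includes noise that no recruiter can foresee. The calculation uses the plan's two-sample t-test rather than the mixed model, so b should be read as the imbalance left after adjustment for baseline WAB AQ.

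**The case against.** A reader might infer that allocation is definitely not concealed because the list holder recruits. The documents do not say so. The qualifier unblinded suggests that there may be more than one coordinator, and several tasks lie elsewhere. The PI contacts most candidates (10.1), and medical intake is done by the PI or a second neurologist (6.1). A co-investigator and a speech pathologist at another institute are to recruit about 8 to 9 subjects a year (4.5). Over the five-year study that is at most 40 to 45 of 83, about half. This narrows the route to selection, and it stands. It does not close the route, because no sentence keeps the unblinded coordinator out.

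A reader might also infer that the list holder could move subjects between severity strata. Section 5.3 keeps those who administer and score the language measures blinded, and no section gives the coordinator a part in WAB scoring. That reading is not supported. What remains open is timing and enrolment.

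Nor would every imbalance go unnoticed. Section 8.4.1 plans secondary analyses adjusted for imbalanced covariates and for named variables including lesion size. That helps with measured features. Chronicity appears only among the candidate predictors in section 8.4.2, and unmeasured features such as motivation appear nowhere.

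Finally, the illustrative error rates rest on assumed imbalances. They show sensitivity and do not estimate bias in this trial.

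**Conclusion.** The point holds in this form: concealment is neither described nor assured. For both studies the documents establish that one unblinded person makes the list, holds it and treats, with no stated safeguard that binds that person. For the main study they leave open whether the same person recruits and pre-screens. If so, selection with knowledge of the next assignment is possible; if not, the weakness is one of documentation and of having no independent custody of the list. For the sub-study no recruiting role can be inferred.

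The size of any bias is unknown. The range of about 7% to 23% for type I error depends entirely on assumed imbalances of 0.1 to 0.3 SD, the planned SD of 5.7 and a 50:25 split. The stated sample size and power are not in question. The trial is presented as a double-blind efficacy test leading to Phase 3, so this is a weakness worth removing while it is cheap to do so.

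**What to change.** - **List.** In 3.1.4 and 3.2.4, have a BAC statistician generate the sequence (stratified in the main study). This statistician should have no subject contact and should not handle the blinded trial data or the safety reports, which section 9.7.1 says are blinded.
- **Custody and release.** Hold the list in a restricted allocation system such as REDCap, which the trial already uses for electronic consent. Release each assignment to the TMS operator only after consent and eligibility are confirmed and, in the main study, the stratifying WAB AQ is locked. Name the WAB administration that sets the stratum.
- **Order.** Amend 3.1 and 3.2 so that randomization follows these steps.
- **Separation of roles.** State in 3.1.4, 3.2.4, 4.5 and 4.6 that the unblinded TMS operator takes no part in recruitment, screening, eligibility decisions or consent. Reconcile the single operator in 5.3 with the technicians in 5.5.

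The cost is a few hours of BAC and REDCap set-up, plus some reassignment of existing tasks if one coordinator now does both jobs. If the roles are already separate in practice, documenting that part takes a sentence or two. The targets of 75 evaluable and 83 enrolled stay as they are.
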